2.2.2 Secondary Endpoints

1. The secondary safety endpoints are the following:
 - a. The percentage of subjects experiencing the following events: SAEs, temporally-related AEs, increased risk scores for DVT or PE, TEEs, inhibitory anti-C1-INH antibodies, or clinically significant abnormalities in laboratory assessments (ie, lab abnormalities reported as AEs).
 - b. The percentage of administrations of CSL830 resulting in solicited local AEs (discomfort [eg, pain, burning], swelling, bruising, or itching at the CSL830 injection site).
 - c. The percentage of subjects who have at least 1 solicited local AE (discomfort [eg, pain, burning], swelling, bruising, or itching at the CSL830 injection site).
 - d. The percentage of subjects who become seropositive for HIV-1/-2, HBV, or HCV.

The secondary safety endpoints will be assessed for Treatment Period 1, Treatment Period 2 and Treatment Periods 1 and 2 (together). The secondary safety endpoints will also be assessed for the Extension Period (only) and for the treatment periods overall for subjects who are included in the Extension Period.

2. Efficacy endpoints considered as secondary include the following:
 - a. The percentage of subjects who experience a time-normalized HAE attack frequency of < 1 HAE attack per 4-week period.
 - b. The percentage of subjects who are responders. “Response” is defined as a $\geq 50\%$ relative reduction in the time-normalized number of HAE attacks during treatment with CSL830, compared with the time-normalized number of attacks that is used to qualify the subject for participation in this study (see [Section 4.1.2](#) [inclusion criterion 5]).

The secondary efficacy endpoints will be assessed for Treatment Period 1, and Treatment Periods 1 and 2 (together). The secondary efficacy endpoints will also be assessed for the Extension Period (only) and for the treatment periods overall for subjects who are included in the Extension Period.

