3.3.5 Subject Assessments with the eDiary

Following randomization, subjects will report the following information in the eDiary:

- Details of the administration of CSL830 (i.e., dose, date, start time of injection, location of injection, and needle type used).
- Local reactions at the site of CSL830 administration (discomfort [e.g., pain, burning], swelling, bruising, itching) (yes/no).
- Prodromal symptoms experienced (fatigue, rash, muscle aches, nausea, tingling) (yes/no).
- HAE symptoms experienced (yes/no).
- Day and time of HAE symptom onset.
- Location of HAE symptom(s) from most severe to least severe (face/lips; tongue/inside mouth; throat/voice box; abdominal; genitourinary; extremities [right arm, left arm, right leg, left leg]).
- Location of primary HAE symptom (face/lips; tongue/inside mouth; throat/voice box; abdominal; genitourinary; extremities [right arm, left arm, right leg, left leg]).
- Severity of HAE symptom(s) (mild, moderate, or severe).
- Medication for the treatment of HAE attacks is needed (yes/no).
- If medication for the treatment of HAE attacks is needed:
 - Medication used (Berinert, Kalbitor, Firazyr, C1-INH other than Berinert, fresh frozen plasma, other).
 - Dose administered.
 - Day and time started.
 - Administration of medication by a health-care professional (yes/no).
- AEs (yes/no).
- Other concomitant medication (yes/no).

CCI

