4.7 Safety Analysis

Safety endpoints will be analyzed using the Safety Population as described in [Section 4.1](#).

AE will be classified using the Medical Dictionary for Regulatory Activities (MedDRA) version 18.0.

AEs which have a start date and time on or after the first injection date and time of CSL830 in study CSL830_3002 are considered treatment-emergent AEs. AEs with missing or partial start date or time will also be considered treatment-emergent following the worst case principle unless the partial date clearly indicates that the AE started before first injection date and time.

Only treatment-emergent AEs will be summarized in tables as described in [Section 4.1](#). AEs occurring after the Week 53 Visit and before the Follow-up Visit of Treatment Period 2 or the first visit of the Extension Period will be assigned to Treatment Period 2. AEs occurring between the Extension Period completion visit and the Extension Period Follow-up Visit will be assigned to the preceding treatment of the Extension Period.

Subgroup analyses will be performed for

- Use of any oral Prophylaxis for Treatment of HAE during the study
- Subject roll-over classification (“CSL830-Continuation” Subjects, “CSL830-Interrupted” Subjects, and “CSL830-Naïve” Subjects)

The subgroup “Subjects who use oral agents for the prophylactic treatment of HAE during the study” will only include subjects who are taking their prophylaxis according to protocol.

Notes:

- The above described subgroup analyses will only be done for
 - the overall AE tables for summary measures of safety
 - the primary safety endpoints by actual treatment
- Categories of subgroups will be presented in tables only if there are a minimum number of subjects in the subgroup ($n \geq 5$).
- If a causality assessment is not provided for an AE, that AE will be considered related to the investigational product. A subject having related and unrelated AEs will be counted once in each category, related and unrelated.
- Missing severity or outcome will be classified as “severe” or “not recovered”, respectively.
- A subject having AEs with different severities will be counted once in each severity category.
- A subject with more than one occurrence of the same AE PT will be counted once in the total count for that AEs PT. Similarly, a subject with one or more AEs in a particular SOC will be counted once in the total for that SOC.

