- Summary of subject with solicited AEs (number with solicited AEs, solicited AEs occurring within 24 hours of investigational product administration, with suspected solicited ADR, solicited SAEs, related solicited AEs, AE leading to discontinuation based on adverse event start date, with subcategories for “related” and “not related”, with each severity and outcome of AEs,).
- Incidence of subjects with solicited AEs by SOC and PT.
- Incidence of subjects with solicited SAEs by SOC and PT.
- Incidence of subjects with solicited AEs by severity and SOC and PT.
- Incidence of subjects with solicited AEs by relationship to investigational product and SOC and PT.
- Incidence of subjects with AE leading to discontinuation based on adverse event start date by SOC and PT
- Incidence of subjects with temporally-related solicited AEs by SOC and PT.
- Incidence of solicited suspected ADRs by SOC and PT
- Incidence of injections followed by
 - at least one solicited AE,
 - no solicited AE,
 - 1, 2, 3, 4, 5, 6, 7 solicited AEs, respectively,
 - > 1 solicited AE,

- 1, 2, 3, 4, 5, 6, 7 solicited AEs within 24h after start of injection and no solicited AE after 24 hours,
- by ≥ 1 solicited AE within 24h after start of injection and no solicited AE after 24 hours,
- by > 1 solicited AE within 24h after start of injection and no solicited AE after 24 hours,
- ≥ 1 solicited AE after 24h after start of injection.

The start dates of the solicited AEs will be compared with the start dates of the injections. If there is at least one start date of a solicited AE after the start date of an injection and before the start date of the subsequent injection, the preceding injection will be counted as an injection followed by at least one solicited AE.

The analyses will be repeated for the subgroup of causal relation (related / not related solicited AEs).

- Incidence of subjects reporting
 - injections followed by at least one solicited AE
 - no injection followed by at least one solicited AE,
 - injections followed by 1, 2, 3, 4, 5, 6, 7, > 1 solicited AE,
 - only at least 1 solicited AE within 24 hours after the injection and no solicited AE after 24 hours,
 - injections only followed by 1, 2, 3, 4, 5, 6, 7, > 1 solicited AE within 24 hours after the injection and no solicited AE after 24 hours,
 - only at least 1 solicited AE after 24 hours and before the next subsequent injection,

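### SAP 4.7.2.1 links solicited AEs to injections by strict start-date bounds with no same-day rule, so read literally the injection-level counts omit reactions that start on an injection day

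*SAP*

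**What the plan says.** Protocol 2.2.2 lists as secondary safety endpoint 1b "The percentage of administrations of CSL830 resulting in solicited local AEs". SAP 2.2.1 carries it as the injections followed by at least one solicited AE, and adds a companion count of the subjects who report such injections.

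The attribution rule is in SAP 4.7.2.1, under Solicited AEs. It begins: "The start dates of the solicited AEs will be compared with the start dates of the injections". The lower bound of the window is then set by the condition "If there is at least one start date of a solicited AE after the start date of an injection". The upper bound, which is the date of the next injection, is strict in the same way, and an injection that meets both conditions is counted as followed by a reaction.

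The list that this rule follows also asks for injections by number of solicited AEs, for rows restricted to the first 24 hours, and for a row "≥ 1 solicited AE after 24h after start of injection". The injection analyses are repeated for related and unrelated solicited AEs.

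Elsewhere the SAP is more exact. For treatment emergence, SAP 4.7 takes "AEs which have a start date and time on or after the first injection date and time of CSL830". SAP 3.3.5 has the eDiary record both the date and the start time of each injection.

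**The concern.** The rule is worded in dates, and both of its bounds are strict. A reaction dated on an injection day is not later than that day's injection date. Nor is it earlier than the next injection's date when judged from the previous injection. It therefore falls in no window, and no tie rule rescues it.

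Same-day onset is not a rare edge case for this endpoint. Protocol 9.2.2 grades discomfort after the procedure, and grades swelling against its state at the end of the procedure. A program that follows the sentence literally would drop reactions that the endpoint is meant to count, and the error would run in one direction, towards better apparent local tolerability per injection.

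**Working it through.** **Inputs.** Comparison unit and bounds: SAP 4.7.2.1. Interval between injections, 3 or 4 days: SAP 3.2. Availability of injection time: SAP 3.3.5. Separate AE entry for each symptom: Protocol 9.2.2. The documents state no figure that depends on this rule, so there is none to reproduce.

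**Step 1: apply the rule to a schedule.** Put injections on days 0, 3, 7, 10, 14, 17 and 21, and check onset on each of days 0 to 14.

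- Literal window: injection date < AE date < next injection date.
- Inclusive window: injection date ≤ AE date < next injection date.

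| Onset day | Literal rule | Inclusive rule |
|---|---|---|
| 0, 3, 7, 10, 14 (injection days) | no injection | injections 1, 2, 3, 4, 5 respectively |
| 1, 2 | injection 1 | injection 1 |
| 4, 5, 6 | injection 2 | injection 2 |
| 8, 9 | injection 3 | injection 3 |
| 11, 12, 13 | injection 4 | injection 4 |

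The two rules differ on the five injection days and agree on the other ten.

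**Step 2: test the rule against the rows it serves.** Take an injection at 18:00. A reaction at 10:00 the next day starts 6 + 10 = 16 hours later; one at 20:00 starts 6 + 20 = 26 hours later. Both are one calendar day after the injection, so dates cannot separate the 24-hour rows. If the date rule governed every row, the within-24-hour rows would keep only reactions that start after midnight. If it governed only the row for at least one solicited AE, the within-24-hour count could exceed that total.

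The subject tables could also disagree. A subject whose reactions all began on injection days would appear in the solicited AE incidence tables and also in the row for subjects with no injection followed by a solicited AE.

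**Step 3: can the size be derived?** No. It depends on *s*, the share of truly affected injections whose reactions all start on the injection date. Under the literal rule, reported percentage = true percentage × (1 − *s*). The documents give neither term. Purely as assumptions, with a true value of 10% of injections:

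- *s* = 0.30: 10% × 0.70 = 7%
- *s* = 0.50: 10% × 0.50 = 5%
- *s* = 0.95: 10% × 0.05 = 0.5%

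An assumed onset model does not narrow this. With an exponential lag of mean *m* hours and an injection at hour *h*, the share of reactions starting before midnight is 1 − exp(−(24 − *h*)/*m*). For 08:00 and *m* = 2 this is 1 − exp(−8), close to 100%. For 22:00 and *m* = 12 it is 1 − exp(−2/12), about 15%. These are shares of reactions, whereas the endpoint counts injections. Each symptom is a separate AE, so an injection with one same-day and one later symptom is still counted, and the two shares need not agree.

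**The case against.** The best defence is that start date is loose wording for date and time. The 24-hour rows make sense only with clock times, SAP 2.2.1 defines temporally-related AEs by a 24-hour window, SAP 4.7 uses AE start date and time, and injection times are collected. On that reading a same-day reaction after the injection is counted. A strictly date-based program might also reveal itself through the inconsistent rows described in Step 2. The table shells are a separate document (SAP 5.3) and may settle the matter.

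This stands as evidence of intent. It does not change the text: the counting sentence names dates, the SAP writes an inclusive date-time comparison elsewhere when it wants one, and no other section gives a different attribution rule. Even on the charitable reading, nothing covers a missing AE time here; the missing-time rule in SAP 4.7 concerns treatment emergence only.

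Two stronger inferences are tempting, and the documents support neither. One is that local intolerance is understated across the safety report. It is not: solicited AE incidence by system organ class and preferred term, severity and relationship, the duration summaries, the listings, the events-per-injection and per-year rates, and the primary endpoint on severe solicited AEs do not use this rule. Protocol endpoint 1c, subjects with at least one solicited local AE, can be taken from the incidence tables. The other is that most reactions would be lost. The protocol's account of the previous study's local reactions (Protocol 1.4) covers intensity and resolution, not time of onset.

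**Conclusion.** The point holds as a defect in a stated rule with limited reach. Followed as written, SAP 4.7.2.1 gives no injection credit for a solicited AE dated on an injection day, and it cannot produce the 24-hour rows in its own list. The affected outputs are the injection-level counts behind protocol endpoint 1b, their repetition by causal relation, and the subject counts derived from them.

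The bias is towards undercounting. Its size is not derivable from the documents, and the percentages in the working are illustrations under stated assumptions, not estimates. The text does not show how the tables were programmed, so a reader should not conclude that any reported rate is wrong.

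**What to change.** Replace the counting sentence in SAP 4.7.2.1 with a date-time rule: a solicited AE belongs to an injection if its start date-time is on or after that injection's start date-time and before the start date-time of the next injection. Use the same linkage for the 24-hour rows and for the subject counts.

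Add a convention for a missing AE start time: an AE dated on an injection day is assigned to that day's injection. State that this may misassign a reaction that began earlier that day, before the injection, and report how many AEs were assigned this way.

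The cost is a few sentences of SAP text, plus reprogramming of the injection-level tables if they were coded on dates alone. Injection times are already collected, and SAP 4.7 already relies on AE start times, so no new data item should be needed.

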4.7.2.2 Laboratory findings

The following laboratory parameters will be collected:

Hematology:

Hemoglobin, hematocrit, basophils, eosinophils, erythrocytes, leukocytes, lymphocytes, monocytes, neutrophils, platelets.

Biochemistry:

Alanine aminotransferase (ALT), chloride, gamma glutamyl transferase (GGT), creatinine, lactate dehydrogenase (LDH), glucose, protein, total bilirubin, potassium, albumin, aspartate aminotransferase (AST), urea, calcium, sodium.

Urinalysis:

Bilirubin, blood, erythrocytes, glucose, ketones, leukocyte esterase, nitrite, pH, protein, specific gravity, urobilinogen.

Coagulation:

International normalized ratio (INR), activated partial thromboplastin time (APTT), fibrinogen, D-dimer, F1+2.

Immunogenicity:

Inhibitory and non-inhibitory antibodies specific to C1-INH.

Viral serology:

HIV types 1 and 2, HBV, HCV.

Dipstick Pregnancy testing:

Dipstick Pregnancy tests will be performed.

4.7.2.3 Analysis of Laboratory Findings

Normal ranges will be provided for laboratory tests. Values outside the normal range will be judged as clinically significant or non-clinically significant by the investigator. All abnormal laboratory data considered as clinically significant will be presented as AE.

All continuous laboratory parameters will be plotted against their scheduled assessments visits.

Analyses of haematology, biochemistry, and coagulation parameters will consist of the following:

- Descriptive statistics for baseline and each treatment visit, including changes from baseline to each treatment visit
- Mean values and the SD of the continuous laboratory parameters at each scheduled visit will be plotted against scheduled visits.

Baseline will be the assessment before the first injection (Week 1 Day 1) for all “CSL830-Naïve” and “CSL830-Interrupted” Subjects and “CSL830-Continuation” Subjects who did not complete the assessments at the CSL830_3001 End of Study Visit. For “CSL830-Continuation” Subjects who complete the assessments at the CSL830_3001 End of Study Visit, these assessments will be the baseline. If the baseline value for a subject is missing, no change from baseline will be calculated for the subject.

The number and percentage of subjects without anti-C1-INH antibodies and with anti-C1-INH antibodies (inhibitory, non-inhibitory and inhibitory and non-inhibitory combined) during the study will be summarized overall and for each study visit

Urinalysis, viral serology and pregnancy testing results will be listed only.

Notes:

- All results outside predefined normal ranges will be flagged as high or low in the data listings.
- Clinically significant laboratory values will be flagged in the listings.
- Unscheduled results will be listed only and not included in summary tables.

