- L:** Beginning with the Week 25 Visit and throughout Treatment Period 2, subjects who experience ≥ 3 HAE attacks (as determined per protocol) within an 8-week evaluation period are eligible for CSL830 dose increases in increments of 20 IU/kg (up to a maximum dose of 80 IU/kg). All CSL830 dose increases are optional, and will be made only in subjects who are eligible, at the sole discretion of investigator. An evaluation period for any dose increase is defined as beginning after a dose-stable period (ie, 2 weeks after the initiation or dose increase of CSL830). See [Section 3.2](#) for additional details.
- M:** The subject eDiary will not be collected from subjects at the last visit of Treatment Period 2 (Follow-up Visit) if they plan to participate in the Extension Period.

Schedule of Laboratory Assessments for “CSL830-Continuation” Subjects ^A

	Treatment Period 1							Treatment Period 2							Follow-up ^B
Week	1	5	9	13	17	21	25	29	33	37	41	45	49	53	See Footnote B.
Day	1	29	57	85	113	141	169	197	225	253	281	309	337	367	
Window (days)		± 2	± 2	± 2	± 2	± 2	± 2	± 2	± 2	± 2	± 2	± 2	± 2	± 2	
Study center visit	X		X		X		X	X		X		X		X	X
Telephone contact		X		X		X			X		X		X		
Blood samples: • Hematology • Biochemistry • Coagulation	X ^C		X				X	X		X				X	
CCI	X ^D		X				X	X		X				X	
Blood sample for anti-C1-INH antibody	X ^C						X							X	
Blood sample for viral serology	X ^C						X							X	
Urine sample for urinalysis	X ^C		X				X	X		X				X	
Urine sample for pregnancy test ^E	X		X				X			X				X	

C1-INH = C1-esterase inhibitor; CCI [redacted]; CCI [redacted].

Notes to the Schedule of Laboratory Assessments for “CSL830-Continuation” Subjects:

- A:** “CSL830-Continuation” Subjects are subjects who complete participation in study CSL830_3001 and who continue directly on to participate in the current study (ie, ≤ 1 week between the End of Study Visit of CSL830_3001 and the first visit of CSL830_3002 Treatment Period 1).
- B:** Subjects will attend a Follow-up Visit occurring 14 days (± 3 days) after the final visit in Treatment Period 2 or any visit resulting in study discontinuation, unless informed consent/assent has been withdrawn or if the Extension Period starts prior to the scheduled Follow-up Visit.
- C:** If these assessments are or have been conducted at the CSL830_3001 End of Study Visit, then they do not need to be repeated here.
- D:** CCI [redacted]

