1.2.3 Previous Clinical Experience

Currently, clinical data are available from two studies that were conducted with CSL830: study CSL830_1001 and study CSL830_2001.

Study CSL830_1001 was conducted in healthy subjects in order to compare the safety and PK of intravenously administered CSL830 and Berinert (the currently marketed C1-INH concentrate). CSL830 had acceptable safety and local tolerability profiles. There were no adverse events (AEs) causally related to CSL830 or Berinert, and there were no clinically significant abnormalities in laboratory parameters, viral safety assessments, vital signs, physical examinations, or electrocardiogram results. No anti-C1-INH antibodies were detected in any subject. There were no thromboembolic events (TEEs), and no surrogate markers suggestive of pulmonary embolism (PE) or deep vein thrombosis (DVT) were identified. CSL830 and Berinert also had comparable PK profiles following single-dose, IV administration.

Study CSL830_2001 was conducted in subjects with HAE (type I or II) in order to characterize the PK, pharmacodynamics (PD), and safety of SC administration. Functional levels of C1-INH activity and levels of C1-INH antigen and C4 antigen were achieved with each CSL830 dosing regimen that was tested. Subcutaneous administration of CSL830 of up to 6,000 IU was tolerated with local site events. Safety events were not related to either absolute CSL830 dose or dose per body weight. There was no evidence of a dose-response relationship between the administered dose of CSL830 and the intensity of treatment-emergent adverse events (TEAEs). Inhibitory auto- antibodies to C1-INH did not develop in any of the subjects in the study. Further, there were no TEEs.

The efficacy and safety of SC CSL830 are currently being assessed in a double-blind, randomized, placebo-controlled, crossover phase 3 study (study identifier CSL830_3001) that is enrolling at least 80 subjects with HAE. During participation in CSL830_3001 subjects are randomly assigned to either a 40 IU/kg CSL830 or 60 IU/kg CSL830 treatment sequence. Each sequence consists of 2 consecutive treatment periods. Each subject receives the assigned dose of CSL830 in 1 treatment period and placebo in the other treatment period. Subjects who participate in study CSL830_3001 will be eligible to participate in this long-term safety study if they meet all eligibility criteria (see [Section 4.1](#)).

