4.1.1 Subject Classification

Before subject eligibility can be assessed against the inclusion and exclusion criteria, each subject will be classified into 1 of the following categories:

Treatment Period 1 and Treatment Period 2

- “CSL830-Naïve” Subjects: subjects who did not participate in study CSL830_3001; subjects who participate in study CSL830_3001 but did not receive blinded investigational product as a part of that study.
NOTE: For “CSL830-Naïve” Subjects, the first study visit is the Screening Visit.
- “CSL830-Interrupted” Subjects: subjects who completed participation in study CSL830_3001, but who delay entry into the current study (ie, > 1 week between the End of Study Visit of CSL830_3001 and the first visit of CSL830_3002 Treatment Period 1).
NOTE: For “CSL830-Interrupted” Subjects, the first study visit is the Screening Visit.
- “CSL830-Continuation” Subjects: subjects who complete participation in study CSL830_3001 and who continue directly on to participate in the current study (ie, ≤ 1 week between the End of Study Visit of CSL830_3001 and the first visit of CSL830_3002 Treatment Period 1).
NOTE: For “CSL830-Continuation” Subjects, the first study visit is the first study visit in Treatment Period 1. For these subjects, the last study visit of CSL830_3001 and the first study visit of Treatment Period 1 from CSL830_3002 may occur on the same day.

Extension Period

- “Extension Period” Subjects: subjects from the United States who complete participation in CSL830_3002 Treatment Period 2 and who continue on to participate in the Extension Period.

NOTE: For “Extension Period” Subjects, the last study visit of CSL830_3002 Treatment Period 2 and the first study visit of the Extension Period may occur on the same day.

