3.6 Randomization

A block randomization with 1:1:1-stratification for “CSL830-Continuation” Subjects, “CSL830-Interrupted” Subjects, and “CSL830- Naïve” Subjects will be used to ensure that subjects are randomized in balanced manner to a starting dose of CSL830 of either 40 IU/kg or 60 IU/kg.

Eligible subjects will be randomized to 1 of the 2 treatment groups (CSL830 40 IU/kg or CSL830 60 IU/kg) by means of Interactive Response Technology (IRT) according to the above mentioned randomization scheme. The IRT will assign the appropriate study treatment to each subject.

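### The laboratory baseline for Continuation subjects mixes samples taken on and off CSL830, so the pooled within-arm change from baseline is hard to interpret without a split by roll-over class

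*SAP*

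**What the plan says.** **Baseline rule.** In SAP 4.7.2.3, Naive and Interrupted subjects take their laboratory baseline on Day 1 before the first injection. So do Continuation subjects without laboratory results from the last CSL830_3001 visit. For Continuation subjects "who complete the assessments at the CSL830_3001 End of Study Visit, these assessments will be the baseline". This is the expected route, because the protocol's laboratory schedule for Continuation subjects states (footnote C): "If these assessments are or have been conducted at the CSL830_3001 End of Study Visit, then they do not need to be repeated here".

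**Timing.** Protocol 4.1.1 defines Continuation subjects by a gap of "≤ 1 week between the End of Study Visit of CSL830_3001 and the first visit of CSL830_3002 Treatment Period 1", and the schedule of events asks for both visits on the same day where possible.

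**Prior exposure.** Protocol 1.2.3 describes CSL830_3001 as a crossover: "Each subject receives the assigned dose of CSL830 in 1 treatment period and placebo in the other treatment period".

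**Planned summary.** SAP 4.7.2.3 plans "Descriptive statistics for baseline and each treatment visit, including changes from baseline to each treatment visit", together with plots of means and SDs by visit. The coagulation panel (SAP 4.7.2.2) is "International normalized ratio (INR), activated partial thromboplastin time (APTT), fibrinogen, D-dimer, F1+2". Table columns are 40, 60 and ≥ 40 IU/kg (SAP 4.1).

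**Subgroups.** SAP 4.7 lists roll-over class as a safety subgroup, then restricts it: "The above described subgroup analyses will only be done for" two outputs, the overview adverse event tables and the primary safety endpoints by actual treatment. Laboratory data are outside both. Protocol 11.3.3 had announced a safety split by participation in CSL830_3001 without that restriction. SAP 4.14 records the dropping of the age and prior IV C1-INH safety subgroups but does not mention this narrowing.

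**The concern.** A change-from-baseline table is normally read as the shift after starting the drug. Here that reading holds only for subjects whose baseline sample was off CSL830. A Continuation subject whose second CSL830_3001 period was active may still be at or near on-treatment exposure when the baseline is drawn. The change then compares one on-drug state with another.

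The planned tables average these subjects with placebo-last Continuation, Interrupted and Naive subjects and offer no way to separate them. A mean change near zero could mean that CSL830 does not move the marker, or that part of the group was already on it at baseline. The study has no untreated arm, so within-arm change is the planned summary in which a modest shift common to both doses would show. The coagulation panel is where this matters most, since thromboembolic events are a named risk (Protocol 1.4) and a primary endpoint.

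**Working it through.** The plan gives no figure for the laboratory baseline, so there is none to reproduce.

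**Inputs**
- c: share of subjects whose baseline is the CSL830_3001 End of Study sample. Not stated. Illustrative values are 0.25, 0.30, 0.50 and 80/110 = 0.727. The last combines the planned minimum of 80 subjects in CSL830_3001 (Protocol 1.2.3) with the approximately 110 to be randomized here (Protocol 3.5). It needs 80 subjects to complete CSL830_3001 and enter within 1 week, so it is a deliberately high value.
- h: share of those whose last CSL830_3001 period was active. Not stated; 0.5 if period order was balanced, shown for 0.4 to 0.6.
- r: fraction of the drug effect still present at the End of Study Visit. Not stated; shown for 1, 0.5 and 0.

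**Formula.** Suppose the true off-drug to on-drug change is Δ, and the effect at baseline is of the same size as on study (equal dose). An active-last Continuation subject shows Δ(1 − r) and everyone else shows Δ. The pooled fraction retained is 1 − c·h·r.

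**Results at h = 0.5**

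| c | r = 1 | r = 0.5 | r = 0 |
|---|---|---|---|
| 0.25 | 1 − 0.125 = 87.5% | 93.8% | 100% |
| 0.30 | 1 − 0.15 = 85% | 92.5% | 100% |
| 0.50 | 1 − 0.25 = 75% | 87.5% | 100% |
| 0.727 | 1 − 0.364 = 63.6% | 81.8% | 100% |

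With r = 1, moving h from 0.4 to 0.6 gives 90% to 85% at c = 0.25, 80% to 70% at c = 0.50, and 70.9% to 56.4% at c = 0.727. Within Continuation subjects alone (c = 1, h = 0.5, r = 1), half the change is retained.

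**Unequal dose.** Continuation subjects are randomized again on entry. Suppose the effect is proportional to dose, r = 1, and active-last subjects come evenly from 40 and 60 IU/kg, so their baseline averages 50 units. With h = 0.5:
- 40 IU/kg arm: active-last subjects change by 40 − 50 = −10 and placebo-last by 40. The mean is 15 instead of 40 (37.5% retained).
- 60 IU/kg arm: active-last subjects change by 60 − 50 = 10 and placebo-last by 60. The mean is 35 instead of 60 (58.3% retained).
- Difference between arms: 35 − 15 = 20, equal to the true 60 − 40 = 20.
- A subject going from 60 to 40 IU/kg changes by 40 − 60 = −20, a reversed sign.

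**The case against.** The strongest reply is that none of c, h or r is in the documents, and neither is any effect of CSL830 on a coagulation marker. If CSL830 does not move these markers, or the effect has gone by the End of Study Visit, nothing is understated. Protocol 1.2.3 reports no clinically significant laboratory abnormalities in the healthy-volunteer study and no thromboembolic events in either earlier study. This stands. It makes the size conditional but does not make the mixed baseline interpretable.

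Second, other parts of the plan do not depend on this baseline. Out-of-range flags, clinically significant values reported as adverse events, risk scores with confirmatory imaging, and the thromboembolic endpoints are untouched. The SAP also specifies "A block randomization with 1:1:1-stratification for" the three roll-over classes, so the randomized 40 versus 60 IU/kg difference in change is not biased in expectation. This stands too, but that difference cannot show a shift common to both doses. Means by visit help little, because the starting value against which they are read is the same mixed baseline.

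Third, change since entry to CSL830_3002 is a legitimate description, and the analysis is secondary and descriptive. True, but the table should then say so.

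A reader might go further and infer that half of these baselines are on drug, that change is therefore diluted, and that a real prothrombotic shift could look absent. The documents do not support that. Half is an inference from an assumed balanced order. Even at the deliberately high share of 0.727, the equal-dose, balanced-order calculation leaves 63.6% of the shift visible. A reader might also take Naive subjects as an untreated reference. They are naive to CSL830, but Protocol 4.1.2 admits Naive subjects on routine IV C1-INH prophylaxis and Protocol 7.2 permits it during Screening.

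**Conclusion.** The concern holds in a limited form. The SAP pools laboratory baselines taken after an active CSL830 period with baselines taken off CSL830, and it plans no table that separates them. Confidence in that is high, because it follows directly from the baseline rule, the crossover design and the 1-week limit.

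Confidence in the size is low to moderate. An understatement arises only if CSL830 shifts the marker and the shift persists at the CSL830_3001 End of Study Visit. Under balanced order, full effect and equal dose it is half the Continuation share. If the effect depends on dose, the loss differs by arm and some individual changes can reverse sign. The issue is confined to within-arm change in hematology, biochemistry and coagulation. No primary endpoint or sample size is affected, so this is a worthwhile, inexpensive improvement to a descriptive safety analysis.

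**What to change.** In SAP 4.7.2.3:
- Add change-from-baseline tables for coagulation, hematology and biochemistry by roll-over class. The class is already a randomization stratum (SAP 3.6) and a split in the demographic tables (SAP 4.4).
- Where the CSL830_3001 treatment sequence is available to the analysts, split Continuation subjects by last-period treatment, active or placebo. The documents do not show whether it is available.
- Footnote the pooled table as having a mixed on/off-CSL830 baseline.
- Describe Naive subjects as CSL830-naive, not untreated, and identify those on IV C1-INH prophylaxis at screening.

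Repeating the draw on Day 1 would not solve this by itself, because Day 1 falls at most 1 week after the CSL830_3001 sample. The cost is SAP wording and a few extra descriptive tables with smaller groups. No new samples are needed.
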